9.4.3. Supportive Analyses of the Primary Endpoint(s)/Outcome(s)

90-min C-peptide measured at screening and , 12 months and 24 months in the different treatment groups will additionally be fit to a mixed linear regression model, allowing estimation and testing of means and differences between groups at each time point, while simultaneously accommodating the correlation arising from the longitudinal study design in estimates of variances used in tests of significance. We will also estimate and test the differential rate of change in mean 90-min C-peptide over time between these groups, by incorporating an interaction term between time point and treatment group into the models. Although this investigation is not specifically powered to test this interaction, this might provide us with useful insight as to the differences in the effect of combination therapy over time on 90-min C-peptide.

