5.2. Randomization

Individuals complying with all inclusion and exclusion criteria and consenting to study participation will be randomized at the clinical site. A blinded statistician will create color and number coded envelopes using a stratified blocked randomization (new diagnosis vs established, child vs adult). Each envelope will contain a card with the corresponding treatment group assignment. Envelopes will be kept in a file cabinet in a secured room at the Diabetes Research Institute. The study PI will perform the randomization of all newly enrolled subjects in a 1:1 ratio to each of the two arms by selecting the corresponding color and number coded envelope to ensure these factors are equally distributed across the two arms of the intervention.

For each subject, the Subject Identificaton Number (SIN), treatment and participant's name will be entered into the study log.

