9.4.4. Descriptive Analyses

In addition to the detailed statistical analysis described above, descriptive analysis will include reporting and comparison baseline characteristics of the study subjects to evaluate whether any substantial differences exist between the vitamin D alone and combination treatment groups for key variables such as age, gender, BMI, HbA1c, baseline C-peptide, insulin requirements and other variables such as concomitant use of other medications to determine any potential bias. These will involve standard two sample comparisons such as T-tests for continuous variables (possibly transformed when necessary to preserve distributional assumptions) and Chi-square or Fisher's exact tests for categorical variables. As described earlier, potentially confounding factors arising from imbalance will be included into more formal statistical models of the investigation.

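### The only continuous C-peptide model (9.4.3) leaves out the stratification factors and does not say how its rate of change treats the on- and off-treatment years

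*Combined protocol and SAP*

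**What the plan says.** Section 9.4.3 takes "90-min C-peptide measured at screening and , 12 months and 24 months in the different treatment groups" and says that these data "will additionally be fit to a mixed linear regression model". It describes that model as "allowing estimation and testing of means and differences between groups at each time point". A further step is to "estimate and test the differential rate of change in mean 90-min C-peptide over time between these groups". The device for this is an arm-by-time-point interaction, and the section adds that the trial is not powered for it. It names no covariate, coding of time, covariance structure or outcome scale.

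Other sections bear on this:

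- Section 5.2 specifies a "stratified blocked randomization (new diagnosis vs established, child vs adult").
- Section 9.4.2 adjusts the primary logistic model for age and time since diagnosis, partly for precision. It does not extend this to 9.4.3.
- Section 9.4.4 lets factors into the formal models when imbalance is found. Transformation is mentioned only there, for baseline comparisons: "possibly transformed when necessary to preserve distributional assumptions".
- Sections 4.3 and 4.9 give one year of treatment, then a year of follow-up off treatment to see whether any benefit lasts.
- Section 5.4.1 describes C-peptide decline after onset as biphasic and steeper in the first year.

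**The concern.** The primary endpoint and the AUC endpoint (9.2) are both reduced to a yes/no comparison with baseline. The 9.4.3 model is the one planned place where the size of a C-peptide difference is estimated. With 56 participants (4.6), its precision and its target both matter.

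Two things are at stake. First, if strata change at different rates, leaving them out puts that spread into the residual and widens the interval for the treatment effect. The clause in 9.4.4 is no remedy: it responds to imbalance, and stratified blocks are there to prevent imbalance in these two factors. Second, a single rate of change over 0, 12 and 24 months joins a year on treatment to a year off it. Depending on how time is coded, it may say little about month 12, the visit at which the primary hypothesis is set.

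**Working it through.** The plan gives no figure for this model. Its one sample-size figure, 12 per group in 9.7, concerns proportions and plays no part here.

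**1. Strata that differ in 12-month change**

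Inputs from the plan: 56 participants, 28 per arm (4.6); four groups of 14 (1.1), so 7 per arm in each. Assumed, because the documents give no C-peptide SD: within-stratum SD of change σ = 0.4; gap g in mean change between new-onset and established groups of 0.2 to 0.8, which is 0.5 to 2 SD; complete data.

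Standard error with strata: 0.4 × √(2/28) = 0.107. Without strata, half the sample sits g/2 above the overall mean and half g/2 below, so the residual variance is σ² + (g/2)². The inflation is √(1 + (g/2)²/σ²).

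| g | Formula | SE inflation |
|---|---|---|
| 0.2 | √(1 + 0.01/0.16) | 3% |
| 0.4 | √(1 + 0.04/0.16) | 12% |
| 0.6 | √(1 + 0.09/0.16) | 25% |
| 0.8 | √(1 + 0.16/0.16) | 41% |

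A simulation of 20,000 trials per setting gave 3%, 12%, 26% and 43%; the small excess is a finite-sample effect. With an assumed true effect of 0.3 and a two-sided 5% test (also assumed), unadjusted power was 77%, 71%, 62% and 48%, against 78–79% adjusted. Unadjusted type I error was 4.5%, 2.8%, 1.6% and 0.5%: conservative, not inflated.

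This gap is in change. Stratum main effects alone largely cancel from a change contrast, so the gain needs strata-by-visit terms.

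**2. Strata that differ by a constant amount over time**

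Let strata explain a share R² of variance at each visit, let r be the within-stratum correlation between baseline and month 12, and suppose the model constrains the arms to a common baseline mean. Residual variance with strata is (1 − R²)(1 − r²). Without strata it is 1 − [R² + (1 − R²)r]². R² and r are assumed.

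- R² = 0.4, r = 0.5: √(0.45/0.51) = 0.94, a 6% reduction in SE.
- R² = 0.2, r = 0.8: √(0.288/0.2944) = 0.99, a 1% reduction.

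Baseline C-peptide already carries most of a constant stratum difference.

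**3. What a single linear rate of change measures**

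With times 0, 1 and 2 years and complete data, the least-squares slope weights are (−1, 0, 1)/2 = (−0.5, 0, +0.5). Month 12 gets zero weight. Generalised least squares gives the same weights under compound symmetry, AR(1) and a random intercept with random slope. One unstructured example (correlations 0.7, 0.6 and 0.8 for visits 1–2, 1–3 and 2–3) gave (−0.42, −0.17, +0.58).

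For an assumed arm difference of 0.20 at month 12:

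| Difference at month 24 | Linear slope difference per year, −0.5/0/+0.5 weights | Year-1 contrast, categorical visit |
|---|---|---|
| 0.40 (keeps growing) | 0.20 | 0.20 |
| 0.20 (fully kept) | 0.10 | 0.20 |
| 0.10 (half kept) | 0.05 | 0.20 |
| 0 (all lost) | 0.00 | 0.20 |

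With categorical visit the month-12 and month-24 contrasts separate. A joint arm-by-visit test, on (2 − 1) × (3 − 1) = 2 degrees of freedom, would still pool the two periods.

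**The case against.** The strongest reply is that 9.4.3 already provides most of what is wanted. It promises group differences at each time point and defines the interaction by time point. With three discrete visits, that fits categorical time and yields a month-12 contrast. A reader might infer that the plan's model ignores month 12, or that a benefit fading off treatment would be missed. The documents do not support this: the zero weight needs linear coding, complete data and particular covariance structures, none of which is stated. Nor does any section treat the slope as the treatment effect; 9.4.2 and 9.6 place that at one year, and looking at the off-treatment year is a declared aim in 4.3. What stands is that rate of change is the language of a slope, and the coding is left open.

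A reader might also put the gain from strata at 11% to 23%, from 1 − √(1 − R²) with R² of 0.2 to 0.4. That applies to a raw difference at one visit with no baseline adjustment, not to a change contrast or a baseline-constrained model. Nor do the documents show that the strata separate high from low C-peptide: they give no levels by age or duration group.

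Finally, age and time since diagnosis do enter the primary logistic model. That shows the sponsor's reasoning, but it does not carry over to 9.4.3.

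**Conclusion.** The point holds as a gap in specification with a modest to material cost in precision. The two stratification factors are missing from the only continuous C-peptide analysis, and no other clause reliably brings them in. The cost is wider intervals and conservative tests, not bias. Its size rests on assumed values: about 3% to 41% on the standard error of the 12-month change contrast for stratum gaps of 0.5 to 2 SD in change, the upper end being a large gap; and about 1% to 6% in a baseline-constrained model if stratum effects are constant over time. The biphasic decline in 5.4.1 makes different rates of change plausible for new-onset against established disease; it says nothing about children against adults.

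The rate-of-change wording needs clarifying; it is not a demonstrated error. The missing transformation is a minor specification point: a reader might infer that a log scale is required, but the documents give no C-peptide distribution from which to judge. The primary test is unaffected.

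**What to change.** In 9.4.3, specify visit as categorical with arm, arm-by-visit, both stratification factors and strata-by-visit terms. Name the month-12 arm contrast as the on-treatment estimate and the month-24 contrast as a separate measure of persistence, and drop the single rate of change. State the covariance structure and the outcome scale in the same paragraph.

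The cost is SAP wording and a few degrees of freedom. Two additive factors add 2 main effects and 2 × 2 = 4 visit interactions. For the 12-month change contrast, residual degrees of freedom fall from 54 to 52, or to 51 if the four strata are entered as separate cells. No extra visits or samples are needed.

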9.4.2. Primary Analysis of Primary Endpoint(s)/Outcome(s)

The metabolic primary outcome is the 90-minute stimulated C-peptide following MMTT, conducted at the 1 year visit. The primary statistical hypothesis to be assessed is that the proportion of patients with maintained or increased level of 90-minute at 12 months as compared to baseline will be greater in subjects receiving combination therapy than for subjects receiving vitamin D alone.

The analysis of the primary outcome will initially involve a two sample test of proportions comparing the proportion of patients in the combination therapy group maintaining or increasing 90-C-peptide with respect to baseline with the proportion of vitamin D alone treated subjects with 90-minute C-peptide that is maintained or increased from baseline value. A covariate-adjusted analysis will additionally be performed by way of a logistic regression model, with a categorical index of treatment group adjusted for baseline age and time since diagnosis; this can provide us with adjustment for potential confounding of these factors and/or provide increased efficiency and precision by including these potentially significant explanatory variables.

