9.7. Sample Size Considerations

Metabolic primary outcome

Sample size considerations correspond to the primary hypothesis which is that the proportion of patients with maintained or increased 90-min C-peptide at 12 months compared to baseline value is greater in the combination therapy group than in the vitamin D alone group. Standard power calculations for two sample tests of proportions indicate that 12 subjects in each group are needed to achieve 80% power to detect differences between less than 5% in the vitamin D alone group and at least 50% in the combination therapy group. Allowing for 10% dropout/attrition, sample size considerations include an allowance for 10% of the subjects to have missing data (one-year MMTT was not done or subject withdrew prior to the one-year assessment).

Primary endpoints should be available for all enrolled subjects. An exception will be if a death occurs or if the subject withdraws consent to be followed, although we expect this to be very limited. We also have included consideration for attrition in our design. Should there be any missing data, missing data will be assessed for mechanism of missingness and to see if missing at random assumptions are valid. If necessary, appropriate imputation strategies can be applied for sensitivity analysis. We will explore the data to assess if missingness at a given time point is related to observed data at the previous time point. If we find that, conditional on treatment group, observed values strongly predict subsequent values where observed, but are not related to missingness at subsequent time points, we may regard the missing data as a random sample of previously observed data.

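### The month-12 arm difference from the Section 9.4.3 mixed model is not adjusted for screening C-peptide, and the plan names no baseline-adjusted one-year estimate

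*Combined protocol and SAP*

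**What the plan says.** Section 9.4.3 takes "90-min C-peptide measured at screening and , 12 months and 24 months in the different treatment groups" and fits all of it to a mixed linear model, "allowing estimation and testing of means and differences between groups at each time point". The model also allows for correlation within participants. Screening is therefore one of the responses, not a covariate. The section then plans a test of differential change between arms "by incorporating an interaction term between time point and treatment group into the models", and says that the study is not specifically powered for it.

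Two other places bear on baseline adjustment. The logistic model for the binary primary endpoint (Section 9.4.2) is fitted "with a categorical index of treatment group adjusted for baseline age and time since diagnosis"; screening C-peptide is not listed. Section 9.4.4 includes baseline C-peptide among the characteristics compared between arms and adds that "potentially confounding factors arising from imbalance will be included into more formal statistical models of the investigation".

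No section enters screening C-peptide unconditionally as a covariate or holds the screening means equal across arms. Section 9.4.3 is the only specified analysis of 90-minute C-peptide as a continuous measure.

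**The concern.** Section 9.5.3 says that the trial aims for a treatment-effect estimate with a 95% confidence interval at one year, using all the information that the design offers. On the continuous scale, the month-12 arm difference in 9.4.3 is the natural candidate for that estimate. Under the usual reading of the text (a separate mean for each arm at each visit), it makes no use of the fact that randomisation gives both arms the same expected screening value. All between-person spread stays in its variance, and any chance difference in screening C-peptide carries through in proportion to rho. The trial pools children and adults, and new-onset disease with disease of up to 10 years, so persistent between-person spread is plausible. At stake is the precision of the one-year supportive estimate in a 56-person pilot.

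**Working it through.** **The plan's own figure.** The documents give no precision or power for the mixed model. The only sample-size figure, in Section 9.7, is that "12 subjects in each group are needed to achieve 80% power" for "differences between less than 5% in the vitamin D alone group and at least 50% in the combination therapy group", and it concerns the test of proportions. It reproduces with unpooled variance and two-sided 0.05: (1.960 + 0.842)² × (0.05×0.95 + 0.50×0.50) / 0.45² = 11.5, so 12. It also reproduces with pooled variance and one-sided 0.05. Pooled two-sided gives 15. Nothing below alters it.

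**Inputs.**
- Arm size: 28 per arm (Section 4.6) with 10% loss (Section 9.7): 28 × 0.9 = 25.2, taken as 25.
- Two-sided 0.05: assumed. The documents state 0.05 only for the safety comparison in 9.5.2.
- Rho: assumed, range 0.3 to 0.9.
- Equal variance at screening and month 12, and complete data: assumed.
- Effect of 0.5 SD: assumed, for illustration.

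**Step 1: what the month-12 difference is.** With a free mean for each arm and visit and no missing data, modelling the correlation does not move the month-12 contrast. In 300 simulated random-intercept fits at each of rho 0.5, 0.7 and 0.8, the largest gap between the model's month-12 difference and the raw difference in means was about 2e-15.

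**Step 2: variances**, in units of 2σ²/n:
- raw month-12 difference: 1
- arm difference in change, month 12 minus screening: 2(1 − rho)
- adjusted for screening (covariate or equal screening means): 1 − rho²

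The variance saving from adjustment is therefore rho² against the raw difference. Against the change contrast it is 1 − (1 − rho²)/[2(1 − rho)] = (1 − rho)/2. A generalised-least-squares calculation gave the same variances under compound-symmetry and AR(1) correlation.

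**Step 3: power.** With f the variance factor from step 2, power = Φ(0.5/√(f × 2/25) − 1.96). Here √(2/25) = 0.283 and 0.5/0.283 = 1.768. For example, at rho 0.7 adjusted: 1.768/√0.51 = 2.476, and Φ(0.516) = 70%.

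| rho | Variance: raw / change / adjusted | Saving v raw | Saving v change | Power: raw / change / adjusted |
|---|---|---|---|---|
| 0.3 | 1.00 / 1.40 / 0.91 | 9% | 35% | 42 / 32 / 46% |
| 0.5 | 1.00 / 1.00 / 0.75 | 25% | 25% | 42 / 42 / 53% |
| 0.7 | 1.00 / 0.60 / 0.51 | 49% | 15% | 42 / 63 / 70% |
| 0.9 | 1.00 / 0.20 / 0.19 | 81% | 5% | 42 / 98 / 98% |

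At rho 0.7, the difference detectable with 80% power is 0.79 SD (raw), 0.61 SD (change) and 0.57 SD (adjusted).

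**Step 4: what the conditional rule in 9.4.4 can miss.** With 28 per arm, a baseline t-test reaches p < 0.05 only at about 2.005 × √(2/28) = 0.54 SD. A screening imbalance of 0.4 SD would not be flagged by that test. At rho 0.7 it would shift the raw month-12 difference by 0.7 × 0.4 = 0.28 SD. It would shift the change contrast the other way, by (0.7 − 1) × 0.4 = −0.12 SD.

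**The case against.** The strongest reply is that screening C-peptide is already in the model. If time is categorical, the month-12 part of the time-by-treatment term is the arm difference in change from screening. That contrast removes persistent between-person spread and subtracts any screening imbalance. This stands. A reader might infer from the month-12 difference alone that the plan's only continuous analysis throws away most of its precision, or that a real effect would be hidden by baseline spread. The documents do not support that: at rho 0.7 the gain over the planned change contrast is 7 points of power (63% to 70%), not 28, and at rho 0.9 it is negligible. Where a participant's change is unrelated to the screening level, the change contrast performs as well as the adjusted one.

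Three limits on this reply remain. Section 9.4.3 describes a differential rate of change over screening, 12 and 24 months and does not name the month-12 component as the one-year estimate. It does not say whether time is categorical or linear; a linear slope would mix the treatment year with the untreated second year. And below rho 0.5 the change contrast is less precise than the raw difference.

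A second reply is that 9.4.4 lets baseline C-peptide into the models. It does, but only after imbalance is seen, and without a stated threshold.

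A third is that the model is loosely described, and equal screening means might be intended. If so, it would already have the precision asked for, but the text does not say so. With missing month-12 values, even the unconstrained model draws some information from screening.

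**Conclusion.** The point holds in a limited form. The month-12 arm difference in 9.4.3 is unadjusted for screening C-peptide on the natural reading, and no pre-specified contrast is both baseline-adjusted and named as the one-year estimate. Against the raw month-12 difference the loss is small at rho 0.3 and large from about 0.7 upward. Against the change contrast it runs the other way: 35% of variance at rho 0.3, falling to 5% at 0.9. Baseline adjustment is the most precise of the three at every rho shown, so it removes the need to guess which contrast will do better.

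These sizes rest on an assumed rho, equal variances at the two visits, complete data, 25 per arm and two-sided 0.05. This is a supportive analysis. The primary comparison of proportions, already defined against each participant's own baseline, and the sample size are unaffected.

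**What to change.** Add to Section 9.4.3 either (a) that time is categorical and the screening mean is constrained to be equal in the two arms, or (b) that screening 90-minute C-peptide is a covariate, with months 12 and 24 as the responses. Then name the month-12 arm difference with its 95% confidence interval from that model as the supportive one-year estimate, whether or not baseline imbalance is seen.

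The cost is a sentence or two in the analysis plan. Screening C-peptide is already scheduled for every participant in Appendix A, so no new data are needed.

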9.4.4. Descriptive Analyses

In addition to the detailed statistical analysis described above, descriptive analysis will include reporting and comparison baseline characteristics of the study subjects to evaluate whether any substantial differences exist between the vitamin D alone and combination treatment groups for key variables such as age, gender, BMI, HbA1c, baseline C-peptide, insulin requirements and other variables such as concomitant use of other medications to determine any potential bias. These will involve standard two sample comparisons such as T-tests for continuous variables (possibly transformed when necessary to preserve distributional assumptions) and Chi-square or Fisher's exact tests for categorical variables. As described earlier, potentially confounding factors arising from imbalance will be included into more formal statistical models of the investigation.

9.5. Interim Analyses

The DSMB will be convened to review safety and efficacy data. Descriptive interim analyses will include distributions of endpoints, and adverse events. Interim analyses will be conducted periodically during the study and will be reviewed by the DSMB for assessment of effectiveness and safety. Group-sequential spending function with an O'Brien-Fleming boundaries may be used to protect the type I error probability from early and multiple testing and to assess the significance of the interim results that emerge during the trial.

9.5.1. Interim Analysis of Efficacy Data

Interim analysis for efficacy will be planned when half the subjects have reached their endpoint. However we note that this is a small trial and if we were to consider a priori planning for interim analysis the limited number of observations could lead to unstable estimates of efficacy. This can be further discussed with the DSMB. The inflation factor needed for augmenting sample size to preserve power if we were to plan for interim analysis at one look with group sequential methods using standard Obrien-Fleming boundaries is 1.02, which does not significantly affect the parameters of our design (sample size needs to be inflated by 1.02).

